Control: This is a pilot proof of concept study with sample size insufficient for a formal randomized comparison. In order to have a valid comparator, participants will be randomly allocated to an intervention and control group (approx. 40 per group). No p values will be calculated. Comparisons will be as risk ratios or mean differences with 95% confidence intervals.

Outcomes

Baseline demography and clinical data will be recorded.

Primary: The primary outcome is the combined frequency of adverse device effects and device deficiencies up to discharge from hospital.

Adverse device effects (ADEs) encompass any adverse event with a reasonable causal relationship resulting from insufficient or inadequate instructions for use; problems with the deployment, implantation, installation, or operation of the device; malfunction of the device; or user error or intentional misuse of the device. They will include device deficiencies such as device expulsion / falling out of the uterus, failed maintenance of suction pressure and tube blockage.

A Serious Adverse Device Effect (SADE) is an adverse device effect that has resulted in any of the consequences characteristic of a serious adverse event. An example of this would be the need for further intervention to treat trauma caused by the device (e.g. sutures, laparotomy, etc).

Secondary efficacy outcomes will include:

- 1. Measured blood loss within 30 minutes after insertion (ml)
- 2. Blood loss >500ml
- 3. Blood loss >1000ml
- 4. Efficiency of suction (assessed through ultrasound assessment of residual blood in the uterus at 30 minutes or blood expressed from the uterus after tube removal)
- 5. Blood pressure, pulse and shock index 15 minutes after vaginal birth or caesarean
- 6. Change in routinely collected haemoglobin levels pre delivery to post delivery
- 7. Blood transfusion
- 8. ICU admission
- 9. Death
- 10. Functionality and acceptability:
 - a. Active bleeding from the uterus continuing for more than 10 minutes (main efficacy outcome).
 - b. Any adverse event
 - c. Pain experienced (No pain/Mild /Severe/Unbearable)
 - d. Need for Additional interventions to stop bleeding (e.g. more uterotonics, compressive measures, UBT, laparotomy, hysterectomy)
 - e. Was STUT effectively inserted? (Yes/No/Unknown)
 - f. How easy was it for health care providers to insert the Suction Tube Uterine Tamponade (easy/moderately difficult/Difficult/failed)

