19. Tamponade device inserted? 2=Other tube*; 3=Ellavi; 4 = Other	· ·				
20. Time device inserted:		:			

21. Ease of insertion? 1=easy, 2=mod.diff, 3=difficult		
22. Device stable in uterus? 0=No; 1=Yes		
23. Tube air leak? 0=No; 1=Yes; 3=No tube		
25. Effect of device on exam/mx? 1. Facilitated, 2. Interfered, 3.Neither		
26. Exam obscured by blood from ut: 0=No; 1=Yes		
27. Time bleeding stopped.	:	
28. Time vital signs check (+ 15min)	:	
29. Syst BP mmHg		
30. Diast BP mmHg		
31. Pulse /m		
32. Additional oxytocin 0 = No 1= Yes		
33. Additional erg-/syntomentrine 0 = No 1= Yes		
34. Additional misoprostol 0 = No 1= Yes		
35. Additional tranexamic acid 0 = No 1= Yes		
36. Time blood collection measured (>30 min)	:	
37. Blood volume excluding suction jar (ml)		
38. Blood volume in suction jar (ml)		
39. Blood expelled ex ut. after removal of device or after 30 min in control group (ml)		
40. If bleeding persists, measured blood loss post 30min		
41. Laparotomy 0 = No 1= Yes		
42. Compression sutures 0 = No 1= Yes		
43. Uterine devascularization 0 = No 1= Yes		
44. Hysterectomy 0 = No 1= Yes		
45. Other procedure 0 = No 1= Yes*		
46.ICU admission 0 = No 1= Yes		
47. Organ failure 0 = No 1= Yes*		

48. Death 0 = No 1= Yes		
49. Blood transfusion (number of units RBCs)		
50. First Haemoglobin after bleeding controlled (g/dL)		
51. Highest temperature (deg C)		
52. Endometritis 0 = No 1= Yes 9=Unknown		
53. Other complications 0 = No 1= Yes* 9=Unknown		
53. Date of Discharge (DD/MMM/YY)	/ /	

Completed by (initials) :	Date completed	(dd/mmm/yy)
Completed by (initials) .	Date completed	(dd/IIIIIII/yy

Vaginal birth Clinical checklist (remains in hospital records)

Equity for Suction Tamponade Access to treat postpartum haemorrhage: The ESTA project

	1.	○ Consent signed
	2.	Confirm with Mother that still happy with consent
	3.	Ostudy trolley is available with register, U-STAT suction tubes, working suction
	4.	Clean drape or Maternawell tray available
	5.	\bigcirc Manual suction device ready with vacuum pumped or suction machine pressure set to 100mmHg – block tubing to check
	6.	After baby born position drape/Maternawell tray below the buttocks
Aft	er p	lacenta delivered completely:
	7.	Examine vaginally to exclude major lower genital tract trauma
	8.	O Note the time, 24 hr: H H : M M
	9.	○ Open next numbered envelope and note allocation: ○ STUT* ○ Control
	10.	*Insert U-STAT tube to fundus of uterus and start suction

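### The adverse device effect definition has no general relatedness clause, so read literally, related harm after uneventful use of a working device (most clearly endometritis) does not enter the primary safety outcome

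*Protocol*

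**What the plan says.** The Outcomes section of the Protocol sets the primary outcome: "The primary outcome is the combined frequency of adverse device effects and device deficiencies up to discharge from hospital".

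It describes ADEs as encompassing "any adverse event with a reasonable causal relationship resulting from insufficient or inadequate instructions for use; problems with the deployment, implantation, installation, or operation". The list then ends with "malfunction of the device; or user error or intentional misuse of the device". The next sentence widens the term: "They will include device deficiencies such as device expulsion / falling out of the uterus, failed maintenance of suction pressure and tube blockage".

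Serious events are defined as a subset: "A Serious Adverse Device Effect (SADE) is an adverse device effect that has resulted in any of the consequences characteristic of a serious adverse event". The illustration given is: "An example of this would be the need for further intervention to treat trauma caused by the device".

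Other parts of the Protocol bear on the point:

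- Outcomes, secondary list: any adverse event (item 10b) and pain (item 10c) are secondary outcomes.
- Data management: all adverse events are recorded, related or not.
- DSMC: the committee's main task is to adjudicate causality.
- Clinical Record Form: item 51 is highest temperature, item 52 is "52. Endometritis 0 = No 1= Yes 9=Unknown", and item 53 is other complications.

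**The concern.** In the ADE sentence a causal relationship is necessary but, as written, not sufficient. The event must also result from one of the listed causes, and each of these describes something going wrong with the instructions, the handling, the device or the user. The usual catch-all, an event related to use of the device as such, is absent.

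The sentence that widens the definition adds performance failures only. The primary outcome therefore counts a blocked tube that harmed nobody, while a related infection after trouble-free use has no clear way in. The Methods section says that the trial is designed to assess essential safety. A primary rate that omits part of the related harm would make the device look safer than the recorded data show. Two adjudicators could also class the same event differently, depending on how strictly they read the list.

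**Working it through.** No figure in the Protocol decides this point. It is settled by reading the definition against the kinds of event that can occur.

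**Step 1. Test event types against the wording**

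| Event in a woman given the device | Listed cause or named deficiency that fits | In the primary outcome, read literally? |
|---|---|---|
| Tube blocks, no harm | Named deficiency | Yes |
| Tube falls out, no harm | Named deficiency | Yes |
| Injury from a misplaced or mishandled tube | Deployment problem or user error | Yes |
| Abrasion during an otherwise normal insertion | Deployment problem, on a reasonable reading | Probably |
| Tissue injury at the set suction, device working | Operation problem only if the phrase is stretched | Arguable |
| Endometritis or fever judged related, after uneventful use | None | No |

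**Step 2. Look for another route in**

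- The secondary outcome of any adverse event collects these harms, but not in the primary rate.
- The DSMC judges causality. No sentence says that a judgement of related makes the event an ADE.
- The serious adverse event report template asks for the relation to the intervention, not for a listed cause.
- Form items 51 to 53 collect temperature, endometritis and other complications. No rule ties them to the primary outcome.

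None of these places a related event without a listed cause into the primary outcome.

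**Step 3. Direction and illustrative size**

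Leaving out related events can only lower the count or leave it unchanged. The Protocol does not give the share left out, so the following figures rest on assumptions. Take n = 40 device women, at most one event each, and a true rate of 10% for all related harms and deficiencies together (10% is the level named in the Sample size section). Let f be the assumed share of events with no listed cause.

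- Counted rate = 0.10 × (1 − f)
- Expected count = 40 × counted rate
- Chance of observing none = (1 − counted rate)^40

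| f (assumed) | Counted rate | Expected events in 40 | Chance of none |
|---|---|---|---|
| 0 | 10% | 4 | 1.5% |
| 0.25 | 7.5% | 3 | 4.4% |
| 0.50 | 5% | 2 | 12.9% |
| 0.75 | 2.5% | 1 | 36.3% |

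The table shows how the effect would scale. It is not an estimate of the effect.

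**The case against.** The strongest reply is that the narrow reading is not the only one.

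- **The verb is inclusive.** Saying that ADEs encompass certain events need not mean that they are limited to them. This has some force, but what is encompassed is itself qualified by the list of causes, and the list closes without a general clause.
- **The list is broader than device fault.** Deployment and operation problems plausibly take in insertion trauma and some suction injury without malfunction or misuse. This stands. A reader might infer that every harm from a correctly used, working device falls outside the primary outcome, and the wording does not support going that far. The clear gap is infection or fever after uneventful use.
- **The serious-event example shows the intent.** It mentions trauma caused by the device and sets no further condition. This also stands. A reader might infer that one woman could be a serious adverse device effect and yet not an ADE. The text does not support that, because every serious event is defined as an ADE, and trauma can arise through a deployment problem. The example points to a broader intention and does not prove a contradiction.
- **Nothing is lost, and the procedures test causality.** All adverse events are recorded, and the form items exist. No procedure tells anyone to discard a related event for want of a listed cause, so it is conjecture that the DSMC would do so. This limits the consequence, but it does not put the events into the primary rate.
- **No decision rule is affected.** The trial is exploratory, reports no p values and sets no threshold at which a lower count would change a stated conclusion. That is fair, and it bears on how serious the gap is rather than on whether it exists.

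**Conclusion.** The concern holds in limited form. The ADE definition ties related events to a list of causes and lacks a general clause for events related to use of the device. Applied literally, it leaves related endometritis or fever after uneventful use outside the primary outcome, and arguably tissue injury at the set suction as well. The likeliest explanation is drafting, since the serious-event example implies a wider scope.

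The direction of the effect is towards a lower primary event rate. Its size cannot be derived from the Protocol. A reader might infer that the rate would be halved, for example 2/40 = 5% instead of 4/40 = 10%, but that needs an assumed split of two events with a listed cause and two without, and nothing in the document supplies one. The conclusion rests on the literal reading and on at least one related event occurring without a listed cause. If there is none, the primary rate is unaffected.

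**What to change.** Reword the ADE sentence in the Outcomes section along these lines: an ADE is any adverse event judged related to the device or to its insertion, use or removal, including, but not limited to, events arising from the causes now listed. The present sentence on deficiencies can stay.

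Add one line saying that events among Clinical Record Form items 51 (temperature), 52 (endometritis) and 53 (other complications) in device women count towards the primary outcome when judged related. Events judged unrelated would stay in the secondary outcome of any adverse event, so ordinary postpartum fever would not be swept in.

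Make the change before any event is adjudicated. It needs no new data item and no change to the sample size. The cost is that the observed ADE rate may be slightly higher than under the present wording.

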- g. Did the suction tube remain in place in the uterus until removal (Yes/No/Unknown)
- h. Did the suction tube establish a good seal (no loss of suction) (Yes/No/Unknown)
- Did the suction tube interfere with or facilitate examination for and management of lower genital tract bleeding after vaginal birth (Facilitated/Interfered/Neither/not applicable/Unknown)
- j. Did the suction tube interfere with or facilitate surgical exposure during caesarean birth (Facilitated/Interfered/Neither/Unknown)
- k. Was there any blockage of the suction tube (Yes/No/Unknown)

Recruitment and consent

We plan to approach women at increased risk of PPH awaiting caesarean or induction of labour, pre-labour or in early labour and provide written and/or video information to them. They will be given time to discuss participation with friends and family and then invited to provide signed consent. Consent will be confirmed verbally immediately after birth, prior to device insertion.

Sample size

We aim to use the U-STAT in 40 participants, with a minimum of 25% being vaginal births and 25% caesarean section. 35 participants will provide 90% confidence that the true rate of adverse device effects and device deficiencies is under 10% (+/-10%). The sample is increased to 40 to account for any unexpected procedural difficulties in the first 5 recruits.

Procedures

Participating sites will be supplied with a 'PPH emergency trolley' containing all the supplies needed for STUT and emergency treatment of PPH, as well as forms for screening, enrolment, randomization and data collection. After vaginal birth, the suction tube will be inserted under sterile conditions transvaginally into the uterine cavity. Suction will be applied either with the manual suction device or with a surgical suction unit, set at 100mmHg suction pressure. If there is excessive bleeding which is not controlled by the STUT, the suction tube will be removed and management continued according to local protocols. If effective, the STUT suction will be interrupted every 30 minutes, and removed as soon as bleeding is controlled without suction. All other care will follow local practice. Blood loss will be measured from enrolment until bleeding is controlled (minimum 30 minutes), using a blood collection drape or Maternawell tray, plus blood collected in the UVT suction bottle, surgical suction and swabs.

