Enrolment will take place immediately after birth of the baby when the participant's name is entered in the enrolment register and allocation takes place by opening the next in a consecutively numbered series of opaque sealed envelopes with allocation cards in computer-generated random sequence in balanced blocks of variable size, stratified by mode of birth. Participants will remain in the trial whether or not the intervention is applied, on the 'intention to treat' principle. Good Clinical Practice (GCP) procedures will be followed.

A clinical checklist will be completed by the attending clinician, which will form part of the patient clinical record. Data will be entered onto paper or electronic CRFs by the research staff.

Quality control will be performed on-site: the research staff will be responsible for ensuring that the CRFs are correctly filled out. Completed CRFs will be checked against the original patient records for correct completion. Any discrepancies will be immediately addressed.

Data management

Because of the small number of participants and limited data per participant, complex data entry strategies will not be needed. Data will be entered onto paper or electronic CRF's, checked for accuracy at source, and stored in a locked filing cabinet or password-protected computer. The data will be entered onto an excel spreadsheet and analysed using Epi Info software.

Adverse events and serious adverse events, whether thought to be related to the trial intervention or not, will be recorded by the site PIs on standard adverse events forms which will be submitted to the University ethics committee and DSMC.

Data protection procedures

The following measures will be taken to ensure participant confidentiality:

- Trial data sets for each participant will be identified by a unique ID number, not the participant's name
- The trial register of names and trial ID numbers, and consent forms will be kept separate from the CRFs
- Trial documents will be kept securely under lock and key and will not be accessible, other than to the research teams
- Data will be entered by trial ID number onto a password-protected database to which only trial staff will have access
- The trial report will not contain the names of any participants
- After completion of the trial, the trial documents will be kept under lock and key for five years

Personal information

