	11.	\bigcirc *Insertion of tube; \bigcirc easy, \bigcirc moderately difficult, \bigcirc difficult, \bigcirc Failed, \bigcirc not done
	12.	Alternative Management
	13.	*Time tube insertion procedure completed 24 hr: H H : M M
	14.	*Check tube/balloon stable in uterus Yes / No / Onot used
	15.	Ocontinue routine care including repair of bleeding tears
	16.	*Effect of device on exam/mx of lower genital tract bleeding? Facilitated; Interfered; Neither; Unknown
	17.	○ Note the time per vaginal bleeding stopped. 24 hr: H H : M M
	18.	○ 15 minutes after insertion (10 above) note time 24 hr: H H : M M
		Systolic BP Diastolic Pulse
	19.	○ 30 minutes after insertion, note time. 24 hr: H H : M M
	20.	
		ml ml
	21.	Replace empty tray, expel blood from the uterus by fundal massage (into tray)
	22.	○ Measure blood loss in tray = RESIDUAL
		ml ml
	23.	*disconnect suction. If no bleeding in 10 minutes, remove U=STAT tube
	2/	*If bleeding continues replace empty tray continue suction plus other measure

25. When bleeding stopped, measure blood loss in tray = Secondary blood loss
ml ml
26. *Measure blood loss in suction bottle
ml ml
27.
○ None
The participants will be followed till discharge and the outcome data, as well as any complications, recorded.

Caesarean birth Clinical checklist (remains in hospital records)

Equity for Suction Tamponade Access to treat postpartum haemorrhage: The ESTA project

	1.	○ Consent signed
	2.	Oconfirm with Mother that still happy with consent
	3.	OStudy trolley is available with register, U-STAT suction tubes, working suction
	4.	Clean drape or Maternawell tray available for post-op use
	5.	○ Manual suction device ready with vacuum pumped or suction machine pressure set to 100mmHg – block tubing to check
	6.	\bigcirc After birth of baby, open next numbered envelope and note allocation: \bigcirc STUT* \bigcirc Control
Aft	er p	placenta delivered completely:
	7.	○ Note the time, 24 hr: H H : M M
	8.	\bigcirc *Insert U-STAT tube to fundus of uterus and lower end through cervix and vagina, ask assistant to connect and start suction
	9.	\bigcirc *Insertion of tube; \bigcirc easy, \bigcirc moderately difficult, \bigcirc difficult, \bigcirc Failed, \bigcirc not done
	10.	. Alternative Management
	11.	. *Time tube insertion procedure completed 24 hr: H H : M M
	12.	. Continue uterine closure
	13.	*Effect of device on visualisation for uterine closure? \(\text{Facilitated}; \text{Interfered}; \) Neither; \(\text{Unknown}\)

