	14.	. Time uterus closed 24 hr: H H : M M
	15.	. Measure blood volume in suction bottle = pre-suction volume:
		ml ml
	16.	*Note the time bleeding through suction tube stopped. 24 hr: H H : M M
	17.	. O 15 minutes after placental delivery (7 above) note time 24 hr: H H : M M
		Systolic BP Diastolic Pulse
	18.	. After skin closure, estimate surgical blood loss (excluding U=STAT tube drainage)
		ml ml
	19.	. O In recovery room: Place drape or Maternawell tray under participant's buttocks
	20.	
	21.	. O 30 minutes after placental delivery (7 above), note time. 24 hr: H H : M M
	22.	. Swab vagina and measure blood loss in drape/tray = postop blood blood

23. O Place new tray or drape under participant and express blood from uterus -
Measure blood loss in drape/tray = RESIDUAL blood
ml ml
24. *Disconnect suction, if no bleeding after 10 minutes, remove U-STAT tube. If
bleeding resumes, reconnect suction and manage as per hospital protocol
25. *Measure blood loss in suction bottle
ml ml
26. *Suction tube problems: Fell out; blocked; leaking; Poor suction
○ None

ml

The participants will be followed till discharge and the outcome data, as well as any complications, recorded.

Participant questionnaire (Vaginal birth Intervention group only)

Protocol Title: Equity for Suction Tamponade Access to treat postpartum haemorrhage: The ESTA project			
Site Number:	Subject ID:	Date:(dd/mmm/yy)	
Dear Participant, thank you for assisting us with the ESTA project. Pease would you answer the following questions. There are no right or wrong answers. Please just give us your personal opinions. Please feel free not to answer if you prefer not to.			
Questionnaire		Comment/Notes	
*After the hirth of your ba	by a tubo was	T	
*After the birth of your baby, a tube was inserted to your uterus to help reduce bleeding Please could you describe the pain you experienced? 0=No pain; 1 = Mild pain; 2 = Severe pain; 3 = Unbearable pain; 4 = unsure; 9 = no data			
*Please could you describe when the tube was removed = Mild pain; 2 = Severe pain Unbearable pain; 4 = unsure	d? 0=No pain; 1 u; 3 =		
*Please could you describe overall about the suction tub 0= fine; 1 = uncomfortable b = Unacceptable; 3 = Unbear unsure; 9 = no data	pe procedure? out acceptable; 2		
Thank you for assisting with this questionnaire			

Date completed

(dd/mmm/yy)

Completed by (initials):

Participant questionnaire (Caesarean birth Intervention group only)

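### Blood loss (outcome 1) and the vaginal-birth checklist readings are timed from device insertion, which controls do not have, so the vaginal control window is undefined

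*Protocol*

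**What the plan says.** The Protocol gives several start points for blood loss and vital signs.

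- **Outcomes, secondary 1:** "Measured blood loss within 30 minutes after insertion (ml".
- **Outcomes, secondary 5:** "Blood pressure, pulse and shock index 15 minutes after vaginal birth or caesarean".
- **Procedures:** "Blood loss will be measured from enrolment until bleeding is controlled (minimum 30 minutes".
- **Quality assurance, During recruitment:** "Enrolment will take place immediately after birth of the baby", with the envelope opened at that point.
- **Vaginal birth checklist, items 18 and 19:** "15 minutes after insertion (10 above) note time" for blood pressure and pulse, and "30 minutes after insertion, note time" for the blood-loss reading.
- **Caesarean birth checklist, item 17:** "15 minutes after placental delivery (7 above) note time". Item 21 sets the 30-minute reading from the same event.
- **CRF:** "36. Time blood collection measured (>30 min", with no start named. Item 39 takes residual blood after device removal, or at 30 minutes in controls, again with no start named.

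Under Methods (Control), the randomised arms are to be compared by risk ratios or mean differences with 95% confidence intervals, without p values.

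**The concern.** A between-arm comparison of a volume collected over time needs the same clock in both arms. Here the first-listed efficacy outcome counts from a step that only the device arm undergoes. Staff completing the vaginal checklist for a control must either leave the timing blank or choose their own start. The only controls with a recorded insertion time would be those given some tamponade device (CRF items 19 and 20), which is a selected group.

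The trial randomises so as to have a valid comparator and to give an indication of effectiveness for a later trial. Leaving out p values does not make differently timed readings comparable. Nor can the analysis repair the problem, because a volume read at the wrong moment cannot be recovered afterwards.

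**Working it through.** The plan states no figure to reproduce. The check sets the passages side by side, followed by an illustration of scale.

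**1. Which clock applies where**

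| Place | Start | Stop | Exists in controls? |
|---|---|---|---|
| Secondary outcome 1 | insertion | 30 min | no |
| Vaginal items 18, 19 | insertion | 15 and 30 min | no |
| Caesarean items 17, 21 | placental delivery | 15 and 30 min | yes |
| Secondary outcome 5 | birth | 15 min | yes |
| Procedures | enrolment | bleeding controlled, at least 30 min | yes |
| CRF item 36 | not named | over 30 min | not determined |

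**2. Do items 18 and 19 apply to controls?** The allocation line (vaginal item 9) puts an asterisk on STUT, and the device steps carry the same mark, including insertion at item 10. Items 18 and 19 carry none. Controls are therefore to complete them, counting from item 10, which they skip.

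**3. When is enrolment?** The text under During recruitment puts enrolment and allocation straight after birth. The vaginal checklist opens the envelope at item 9, after the placenta and the examination for trauma. The Procedures start point is therefore itself ambiguous in vaginal births.

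**4. Possible control windows in vaginal births.** Let *d* be the time from allocation to insertion.

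- If controls are timed from allocation, the device reading ends *d* minutes later than the control reading.
- If controls are timed from birth, the device reading ends later by *d* plus the time from birth to allocation.
- If controls are read when bleeding is controlled, as in Procedures, the control window may be the longer one.

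The text does not choose between these.

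**5. Illustration of scale.** The documents give no insertion time, only a description of it as rapid (Table 1). Assume *d* is 2 to 10 minutes and controls are timed from allocation.

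- Relative to a 30-minute window: 2/30 = 7% and 10/30 = 33%.
- The vaginal tray is placed after birth (item 6), and the next tray change that can be read is item 21. If the reading covers everything since birth, and birth to allocation takes an assumed 10 minutes, the ratios are 42/40 = 1.05 and 50/40 = 1.25, so 5% to 25% longer.
- At an assumed 5 to 20 mL/min, the extra volume per vaginal birth is 2 × 5 = 10 mL to 10 × 20 = 200 mL.
- The Sample size section requires at least 25% of each mode in the device arm, so 25% to 75% are vaginal. The shift in the whole-arm mean is then 0.25 × 10 = 2.5 mL to 0.75 × 200 = 150 mL.
- For comparison, the 95% interval half-width with 40 per arm and the SD of 496 mL quoted in the Background is 1.96 × 496 × √(2/40) ≈ 217 mL. That SD is for caesarean birth, so it is only a rough yardstick.

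**6. Where the arms do share a clock.** Both caesarean readings count from placental delivery in both arms. The fault there is only that outcome 1 says something else. For shock index, outcome 5 uses birth, and only the vaginal checklist uses insertion.

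**The case against.** A reader might infer that the arms are measured over different windows throughout, that the device window is always longer, and that blood loss and the >500 ml and >1000 ml outcomes are therefore biased against the device by 7% to 33%. The documents do not support this.

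- Caesarean arms share a window, and outcome 5 is defined from birth.
- In vaginal births the control window is undefined, not shown to be shorter. Under the Procedures stop it could be longer.
- The >500 ml and >1000 ml outcomes carry no time window. Loss after 30 minutes is recorded separately (CRF item 40, vaginal item 25), so a shift of a few minutes would largely drop out of a total.
- The 7% to 33% rests on an assumed delay. It is a share of time, not of blood, and it shrinks if the tray has been collecting since birth.

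Further points also carry weight. Some of the different stops describe different quantities: the CRF separates the reading at about 30 minutes, residual blood and later loss. The wording of vaginal item 20 was lost in extraction, so its exact instruction cannot be judged. The primary outcome (device effects and deficiencies) is untouched, and so is the main efficacy outcome, which concerns bleeding beyond 10 minutes. The protocol promises CRF guidelines, piloting and a final analysis plan before recruitment.

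All of this limits the reach of the point. It does not remove it: outcome 1 and vaginal items 18 and 19 still give a rule that cannot be applied to a control.

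**Conclusion.** The point holds in a limited form. Secondary outcome 1 and vaginal checklist items 18 and 19 use a start that controls lack, and this conflicts with the caesarean checklist, outcome 5 and Procedures. In vaginal births the control window is undefined. Unequal windows are a likely result, but neither their size nor their direction is fixed by the text. The 2 to 10 minute figure and everything derived from it are assumptions given for scale. In caesarean births the fault is a contradiction with outcome 1, and for shock index it is a conflict between the outcome list and the vaginal checklist. Bias in the >500 ml and >1000 ml outcomes is not shown, although what they count should be stated. Severity: should-fix, because only secondary outcomes are affected.

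**What to change.** Before recruitment, adopt one time zero that exists in both arms and does not depend on insertion.

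- Record placental delivery time in vaginal births, as caesarean item 7 already does. Alternatively use the time at vaginal item 8, which precedes allocation and is noted in both arms, and state that it follows the trauma examination and so is not exactly placental delivery. In the caesarean checklist placental delivery comes one step after the envelope is opened but before insertion, so it is still common to both arms.
- Reword outcome 1 and vaginal item 19 to 30 minutes after that time, and vaginal item 18 to 15 minutes after it.
- Align outcome 5 and CRF items 36 and 39 with the same start, and bring the Procedures sentence into line.
- State whether loss >500 ml and >1000 ml refers to the 30-minute or the total measured loss, and whether it includes blood collected since birth.

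The cost is the wording of the outcomes, checklist and CRF items, and at most one extra clock time in vaginal births. No change to sample size or staffing is needed.
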